## 9.7 Safety Analysis

Secondary analyses to examine long-term safety of AFQ056 in this cohort of young children with FXS will be done as follows. Frequencies of adverse events occurring throughout the entire treatment period (both clinical and laboratory) will be tabulated and compared between the active drug and placebo groups during the placebo-controlled period of the study (8 months) and compared across the entire study duration divided based on treatment-assignment at the time of the AE. **Low frequency AEs occurring in less than 5% of the cohort and those that are not different between the drug and placebo groups by visual inspection will not be analyzed further.** Higher frequency events for which statistical comparison would be possible and that appear to be occurring at different frequencies between the drug and placebo groups for either set of comparator groups will be formally compared statistically using a chi-squared analysis. Longitudinal analyses will be done for AEs occurring more frequently in the AFQ056-treated group to determine if there is an increase over time of treatment in these AEs.

[figure not shown]
AFQ056 for Language Learning in Children with FXS

Version v15

Version date 02/03/2021

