take into account differential responsiveness and the known inter-child variability in drug levels with AFQ056, and allow use of the maximum tolerated dose (MTD) where MTD is defined as the maximum tolerated dose of the available dose levels in the protocol, which is felt likely to be most effective. There will be a 4-month single-blind placebo lead in after screening assessments during which subjects will have therapy treatments as usual to control for the effects of the language intervention. The placebo lead-in will also control for placebo effects which are prominent in clinical trials in FXS. This will be followed by an 8-month placebo-controlled phase in which 100 subjects with FXS will have AFQ056 baseline assessments and be randomized 1:1 to AFQ056 or placebo. Dose titration to MTD starting at 25 mg AFQ056/matching placebo will occur over 2 months and then subjects will have language intervention baseline assessments and initiate the language intervention, remaining on a stable AFQ056/placebo dose for the next 6 months. After 8 months of treatment in the placebo-controlled phase (6 months of language intervention), all subjects will have final assessments and will enter the open label extension and be treated with active drug according to the same schedule as in the placebo-controlled phase with 2 months of flexible dose titration to the MTD followed by a period of stable treatment. The duration of the stable treatment will depend on when the subject was enrolled into the study; those enrolled prior to June 15-30, 2019 will receive a 6-month period of stable treatment, and the open label extension may be shortened on a sliding scale for those enrolled after June 15, 2019, such that their treatment including weaning, if necessary, will end before August 31, 2021, with the exact length of the stable treatment period in the extension being determined by how long after June 15 they enroll and what dose of drug they are receiving in the open label treatment period (higher doses will have a longer weaning period of maximally 2 weeks for those on 75-100 mg BID, but 1 week for 50 mg BID, and no weaning period for lower doses). The total duration of the stable treatment for those enrolled after June 15, 2019 will range from 6 months to no open label extension, depending on the number of months after June 15, 2019 the subject is enrolled into the study. As such, some subjects will have an acute dose decrease if they were on a dose of 50-100 mg BID of active drug in the initial phase but experience from the Pediatric PK study conducted previously suggests that children can stop AFQ056 without withdrawal symptoms and the dose decrease and titration in the open label extension are unavoidable to maintain the blind of the study through the completion of the placebo-controlled period by the final participant. The open-label extension will allow all children a period of active drug exposure to make recruitment feasible, despite the long placebo period, and will allow additional collection of long-term safety data. Subjects will continue the language intervention through the extension phase to gain additional data on long-term effects of the combination of AFQ056 and the language intervention on developmental trajectory and the ERP biomarker.

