The study number for the subject and study visit number will be added to the label by the coordinator at each study visit when the study drug is given to the subject. Study drug will be dispensed to subjects at all study visits after screening, until the Follow Up visit, after which no more study drug will be provided. From the month 8 visit on, study drug will no longer be blinded and all subjects will receive active drug. Drug dispensed at the month 8 visit and after will be labeled as AFQ056 and will contain the same information as the AFQ056/placebo labels for bottles dispensed up to month 8. Amount of study drug dispensed during flexible dosing periods will be calculated to accommodate any possible dose increases that would occur prior to the next study visit. All bottles of study medication including empty, partially used and unused bottles will be returned to the study site at each visit, and a new set of bottles will be dispensed.

Study drug will be received at the study site by a designated person, handled and stored safely and properly at the site pharmacy or other designated location, and kept in a secured location to which only the Study pharmacist and staff, site Investigator and designated staff have access. Upon receipt, the study drugs will be stored according to the instructions specified on the drug labels. Storage conditions will be adequately monitored and temperature in the area in which the study drug is stored will be controlled, monitored and recorded, at a minimum on a daily

basis. Appropriate temperature logs will be maintained. For more details, please refer to the Study Medications/Central Pharmacy section of the Manual of Operations.

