### 9.5.3 Other Secondary & Exploratory Outcomes

#### Safety Endpoints

The number of adverse events (AEs) and serious adverse events (SAEs) will be tracked over time. Counts will be statistically compared among the AFQ056 and placebo groups to evaluate safety in regards to whether levels are statistically equivalent over time. This will be looked at separately during the main study phase and extended study phase. In order to evaluate safety, the following will be assessed.

- Safety measures including clinically significant laboratory values and adverse events tabulated for descriptive comparison between the placebo and active drug groups.
- Tolerability, defined as the ability to at least continue treatment after the dose has been reduced to the lowest allowed dose (12.5 mg) due to side effects. The necessity to discontinue treatment after dose reduction to 12.5 mg would be considered lack of tolerability.

**Biomarker Exploratory Outcomes:** Another key secondary objective of this study is to show improvement in specific measures from ERP biomarkers in the combination of the AFQ056/language intervention group relative to those in the language intervention/placebo group. To address this objective, a number of key secondary biomarker endpoints will be obtained:

- ERP
  - Auditory habituation first 15% versus last 15% for amplitude of pediatric p50/N1 (P1) peak occurring at approximately 100 ms post-stimulus
  - Amplitude of auditory response at three components: pediatric p50/N1, N2, and P2
- Eye Tracking
  - Percent of looking time to eyes (all conditions)
  - Number of fixations to eyes (all conditions)

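### The whole-study adverse-event comparison uses a chi-squared test with no allowance for time at risk, although mean exposure can reach 12 months on drug against 8 on placebo

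*Combined protocol and SAP*

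**What the plan says.** Section 9.7 (Safety Analysis) plans two comparisons of adverse-event (AE) frequency between drug and placebo. The first covers the randomized 8-month period. In the second, events are "compared across the entire study duration divided based on treatment-assignment at the time of the AE". Events that look different between drug and placebo "for either set of comparator groups will be formally compared statistically using a chi-squared analysis".

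Two screens come before the test. "Low frequency AEs occurring in less than 5% of the cohort" are dropped from further analysis, and "those that are not different between the drug and placebo groups by visual inspection will not be analyzed further".

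Section 9.5.3 (Safety Endpoints) words the matter differently: "Counts will be statistically compared among the AFQ056 and placebo groups", and "This will be looked at separately during the main study phase and extended study phase". Neither section mentions person-time, exposure-adjusted rates or a time-to-event method.

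On exposure, section 5.2 states: "From the month 8 visit on, study drug will no longer be blinded and all subjects will receive active drug". The Synopsis plans an 8-month extension, but says that stable treatment for children "enrolled after June 15, 2019 will range from 6 months to no open label extension".

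**The concern.** Treatment at the time of the event defines the columns, and after month 8 only the drug column accrues time. A chi-squared test on the share of children with an event treats the columns as if each child had been watched equally long in both. With more months on drug, a common event can look drug-related when its rate is the same on and off drug. Children in the placebo arm (all children, if the lead-in counts) also fall in both columns, so the test's independence assumption fails.

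Sections 2.1 and 9.3 give long-term safety in very young children as a purpose of the extension, and this comparison carries that evidence. No stopping rule uses it. The harm would be a long-term safety report whose p-values partly measure the length of the extension.

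**Working it through.** **Exposure.** The plan's own figures reproduce: 8 + 8 = 16 months maximum on drug (section 2.1), and 4 + 8 + 8 + 1 = 21 months in total (Synopsis). With 50 children per arm, a full extension and no dropout:

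- Drug: 50 × 16 + 50 × 8 = 1,200 child-months over 100 children, mean 12.
- Placebo, lead-in not counted: 50 × 8 = 400 over 50 children, mean 8.
- Placebo, lead-in counted: 50 × 4 + 50 × 12 = 800 over 100 children, mean 8.

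Section 9.9 records AEs from consent, so lead-in events will exist. The plan does not say whether they count as placebo.

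**Event rates.** The 12-week placebo risks in Table 4 (adults and adolescents) convert by −ln(1 − risk)/2.76 months: 1.1% gives 0.0040 per month, 2.3% gives 0.0084 and 7.0% gives 0.0263. A rate of 0.02 was added as an assumed intermediate value.

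**One case by hand.** At 0.02 per month on and off drug, the risk over m months is 1 − exp(−0.02m).

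- Drug: 27.4% (16 months) and 14.8% (8 months), mean 21.1%.
- Placebo: 14.8% without the lead-in. With it, 7.7% (4 months) and 21.3% (12 months), mean 14.5%.

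The columns differ by more than 6 percentage points with no drug effect.

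**False-positive rates.** Simulation used 20,000 trials per setting and an uncorrected chi-squared test on children with at least one event, two-sided 5% (section 9.7 states no alpha). Rates were constant and equal. Ranges run over no frailty and gamma frailty with variance 1, the latter making a child's events correlated across the columns. Dropout is a constant hazard reaching 20% by month 16, since section 4.4.1 expects 80-90% retention. Paired cells are lead-in not counted / counted. Mean months are with the lead-in counted.

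| Extension | Dropout | Mean months, drug v placebo | 0.0084 | 0.02 | 0.0263 |
|---|---|---|---|---|---|
| Full 8 months | 0 | 12.0 v 8.0 | 6-8% / 11-13% | 11-14% / 17-23% | 12-17% / 20-27% |
| Full 8 months | 20% | 10.6 v 7.8 | 6-7% / 9-10% | 9-12% / 13-18% | 10-15% / 15-21% |
| Sliding, mean 6.1 | 0 | 10.1 v 8.0 | – | 6-7% / 7-10% | 6-7% / 8-11% |
| Sliding, mean 6.1 | 20% | 9.0 v 7.8 | – | 6-7% / 6-8% | 5-7% / 6-8% |
| 6 months for all | 0 | 10.0 v 8.0 | – | 5-9% | 6-11% |

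At 0.004 with a full extension and no dropout the figures are 3% / 7%. With 4 months for all (8 v 8) there is no excess (3.4-5.2%). With 2 months for all (6 v 8) the rate is 9-13% at 0.02-0.0263, nearly all favoring the drug. The randomized 8-month test holds its level (2.8-5.6%).

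The sliding scale assumes uniform enrollment over 18 months to February 2020 and a linear fall from 8 months to 0 after June 15, 2019. The Synopsis dates point elsewhere. A child enrolled at the end of February 2020 reaches month 8 at the end of February 2021, about 6 months before drug expiry. If only those dates limit the extension, its mean is 7.9 months and the rates are 10-22% at 0.02 and 11-26% at 0.0263.

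**Unit.** If raw event counts were compared as though both columns had equal time (1,200 v 800 child-months, lead-in counted, Poisson), an event with a 10% 8-month risk would be called worse on drug in 18% of trials.

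**The 5% screen.** If the cohort is 100 children and the count covers only the randomized period, an event at 8% on drug and 0% on placebo misses the cut with probability P(Bin(50, 0.08) ≤ 4) = 0.63. Over the whole study, with all 100 children able to receive drug, this falls to 0.09 if each child's risk is confined to one course, or about 0.006 under a constant hazard and full extension. Section 9.7 does not say which period applies.

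**The case against.** The strongest reply is that this is a drafting gap in a secondary table. Section 9 promises a formal SAP. Section 9.7 lists the unbiased randomized comparison first, section 9.5.3 looks at the phases separately, and section 9.7 adds longitudinal analyses of events more frequent on drug. The upper half of the range needs the lead-in counted as placebo, which is arguable because children have no assignment before visit 3. With the sliding scale and 20% dropout, error is only 5-8%. In Table 4, 20 of 24 placebo rows are at 2.3% or lower and only 3 are at 7.0% or higher (nasopharyngitis, headache, upper respiratory infection).

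Much of this stands as a limit on size: the largest figures apply to few event types and to full or nearly full extensions. It does not remove the fault. The test is stated, and no SAP among these documents replaces it. The longitudinal analyses ask only whether an event increases over time on drug. A flat trend does not separate longer observation from a real, steady drug effect.

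On the screen, the reply is largely right. In the randomized period 4 v 0 gives Fisher p = 0.117, so the cut loses no result that an exact 5% test would have found. What is lost is the effect estimate and its interval.

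**Conclusion.** The concern holds: the whole-study rule in section 9.7 is biased as written. With full or nearly full extensions, a common event with equal rates has about a 9-17% chance (lead-in not counted) or a 13-27% chance (counted) of being reported as different, nearly always as worse on drug. Because the bias shrinks and can reverse as extensions shorten, the result partly reflects enrollment date and drug expiry.

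These sizes assume constant rates, a 5% two-sided test on children, and adult and adolescent event rates. Rates that change with age or time in study would alter the size or direction of the bias. The randomized 8-month comparison is sound. This should be corrected, but it does not threaten the primary analysis or any stopping decision.

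**What to change.** - Limit between-group testing to the randomized 8 months. Report risk differences with 95% confidence intervals (exact where sparse) for every tabulated AE, not only those passing the 5% and visual screens.
- Replace the whole-study chi-squared test with events per child-month by treatment state and phase, with child-clustered intervals, for example a Poisson GEE with a log-exposure offset. In simulation (6,000 trials per setting, full or sliding extension, 0 or 20% dropout) a Poisson rate comparison with that offset and child-clustered variance gave 2.5-5.8% false positives.
- State whether the lead-in counts as placebo and whether the unit is the child or the event.
- Describe the whole-study comparison as non-randomized and confounded by age, time in study and open-label reporting.
- Reconcile section 9.5.3 (phases separate) with section 9.7 (pooled), and the Synopsis enrollment and expiry dates with its statement that some children may have no extension.

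The cost is SAP wording and slightly longer AE tables. No new data are needed.

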Because it will be critical to have the AFQ056 dose titrated to the maximum dose tolerated before initiating the language intervention, there will be a two-month flexible dose titration period before initiating the language intervention to make sure the dose is optimized before the language intervention starts. Thus, the total placebo-controlled period will be 8 months. After the end of the placebo-controlled period, all subjects will initiate titration of AFQ056 as per the titration protocol in the placebo-controlled period, starting with 25 mg BID to the maximum tolerated dose (up to 100 mg BID) over 2 months and then will be treated with AFQ056 through an open label extension. All subjects, families and investigators will remain blinded to treatment status during the placebo-controlled period during the extension period until the final subject has completed the placebo-controlled period and all data from this period is entered in the DCC database and locked. As such, some subjects will have an acute dose decrease if they were on a dose of 50-100 mg BID of active drug in the initial phase but experience from the Pediatric PK study conducted previously suggests that children can stop AFQ056 without withdrawal symptoms and the dose decrease and titration in the open label extension are unavoidable to maintain the blind of the study through the completion of the placebo-controlled period by the final subject.

The purpose of the extension period will be the following:

1. To systematically establish safety of AFQ056 in a larger cohort of subjects (which will include all those treated with placebo in the first period of the trial) and over a longer period of time (up to 16 months in those treated with drug during the first period) in the 3-6 year age group. If AFQ056 were ever to be used for treatment of FXS based on this and other subsequent studies, patients would be treated for life or at least for many years until something better is developed. Although there is safety data over long periods in older patients, there is no extended safety data for young children. Even though we are not predicting specific safety issues, this extended treatment of up to 16 months will help build an important chronic safety profile for future use in very young children.
2. To examine the trajectory of effects of AFQ056 on language development with the language intervention over a longer period of time (14 months) relative to the 6 months in the placebo-controlled period.

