### 3 STUDY DESIGN

The trial will use a double-blind placebo-controlled parallel-group flexible-dose forced titration design in which 100 subjects with FXS, age 32 months to 6 years of age will enter a single-blind 4-month placebo lead-in, followed by an 8-month placebo-controlled phase in which they are randomized 1:1 to AFQ056 or placebo followed by an 8 month open label extension phase in which all participants enrolled by June 15, 2019 will be treated with active drug. For participants enrolled after June 15, 2019, the duration of the open label extension will be shorter and will depend upon when the subject is enrolled and what dose of AFQ056 the participant is taking for stable treatment in the open label extension. The total duration of the stable treatment for those

AFQ056 for Language Learning in Children with FXS

Version v15

Version date 02/03/2021

enrolled after June 15, 2019 will range from 6 months to no open label extension, depending on the number of months after June 15, 2019 the subject is enrolled into the study. The flexible dose design will mimic practice, take into account differential responsiveness and the known inter-child variability in drug levels with AFQ056, and allow use of maximum tolerated dose (MTD) which is likely to be most effective.

Participants will be seen for a screening visit during which they will have assessments (to include language, communication, cognitive, adaptive, behavioral measures, CGI, blood for safety labs and biomarkers, U/A, EKG, ERP and eye tracking) and if they meet entry criteria will start a single-blind 4-month placebo lead-in to provide a control group with treatment as usual for the language intervention placebo group. Subjects will be seen for a study visit 2 months into the placebo lead in (-2 months). It should be noted that although 32 month old children can enter the placebo lead-in, these children will be age 3 years before they are randomized and are potentially exposed to drug, thus the age of treatment will remain within the age range that has been studied in the prior pharmacokinetic study with AFQ056.

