After 8 month assessments in the placebo-controlled phase (including 6 months of language intervention), all subjects will enter the extension and be treated with active drug according to the same schedule as in the placebo-controlled phase. All subjects will be dosed with 25 mg BID of unblinded AFQ056 upon completion of the 8 month visit, followed by 2 months of flexible dose forced-titration to the MTD of the dose levels available in the protocol (dose adjustments to be done as described above for the placebo-controlled period for the flexible dose forced-titration). This will be followed by a period of stable treatment. The length of stable treatment will be dependent upon how long after June 15, 2019 the participant enrolls and what dose of drug they are receiving in the open label treatment period. The total duration of the stable treatment for those enrolled after June 15, 2019 will range from 6 months to no open label extension, depending on the number of months after June 15, 2019 the subject is enrolled into the study.

Some subjects will have an acute dose decrease if they were on 50-100 mg BID of active drug in the initial phase but experience from the PK study suggests that children can come off AFQ without withdrawal symptoms and the dose decrease and titration in the open label extension are unavoidable to maintain the blind of the study through the completion of the placebo-controlled period by the final participant. Subjects will continue the language intervention through the extension phase. The open-label extension will allow all children a period of active drug exposure to make recruitment feasible, despite the long placebo period. It will also allow an assessment of more long term-effects of the language intervention and its impact on the ERP and eye tracking biomarker outcomes and other developmental and behavioral outcomes, will allow examination of the trajectory of the language intervention going from placebo to drug treatment in a blinded setting, and will furthermore allow additional long-term safety data to be collected on a larger cohort of children exposed to AFQ056. A diagram of the study design is provided below in Figure 2.

Figure 2. Effects of AFQ056 on Language Learning in Young Children with Fragile X Syndrome (FXS) – Protocol Design

AFQ056 for Language Learning in Children with FXS

Version v15

Version date 02/03/2021

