## 9.1 General Design Issues

**Trial Design:** The trial will be a phase II double blind placebo-controlled parallel-group flexible-dose forced-titration study that will use a novel design to address the impact of AFQ056 on language learning in 3-6 year old children with FXS. The flexible dose design will mimic practice, take into account differential responsiveness and the known inter-child variability in drug levels with AFQ056, and allow use of the maximum tolerated dose (MTD) where MTD is defined as the maximum tolerated dose of the available dose levels in the protocol, which is felt likely to be most effective. There will be a 4-month single-blind placebo lead in after screening assessments during which subjects will have therapy treatments as usual to control for the effects of the language intervention. The placebo lead-in will also control for placebo effects which are prominent in clinical trials in FXS. This will be followed by an 8-month placebo-controlled phase in which 100 subjects with FXS will have AFQ056 baseline assessments and be randomized 1:1 to AFQ056 or placebo. Dose titration to MTD starting at 25 mg AFQ056/matching placebo will occur over 2 months and then subjects will have language intervention baseline assessments and initiate the language intervention, remaining on a stable AFQ056/placebo dose for the next 6 months. After 8 months of treatment in the placebo-controlled phase (6 months of language intervention), all subjects will have final assessments and will enter the extension and be treated with active drug according to the same schedule as in the placebo-controlled phase with 2 months of flexible dose titration to the MTD followed by a period of stable treatment. The duration of the stable treatment will depend on the month the subject is consented into the study. As such, some subjects will have an acute dose decrease if they were on a dose of 50-100 mg BID of active drug in the initial phase but experience from the Pediatric PK study conducted previously suggests that children can stop AFQ056 without withdrawal symptoms and the dose decrease and titration in the open label extension are unavoidable to maintain the blind of the study through the completion of the placebo-controlled period by the final participant. The open-label extension will allow all children a period of active drug exposure to make recruitment feasible, despite the long placebo period, and will allow additional collection of long-term safety data. Subjects will continue the language intervention through the extension phase to gain additional data on long-term effects of the combination of AFQ056 and the language intervention on developmental trajectory and the ERP biomarker.

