Subjects will be monitored for AEs from the time they sign consent until the final Study visit. If an AE is ongoing or discovered at a subject's final Study visit, the AE will be followed until resolution, or for a minimum of 30 days, whichever comes first. Resolution means that the subject has returned to status at enrollment. If the AE is still ongoing after 30 days, it will be resolved with sequelae. All AEs monitored past the final visit can be followed via telephone – a repeat Termination/Final Follow-up visit does not need to occur.

All SAEs must be followed until resolution throughout the trial. SAEs that are discovered less than 60 days prior to the subject's final Study visit will be followed until resolution or for a minimum of 60 days, whichever comes first, even if it is past the final visit. If a new SAE is discovered at the subject's final Study visit, it must be followed until resolution, or for a minimum of 60 days, whichever comes first. If the SAE is still ongoing after 60 days, it will be resolved with sequelae. All SAEs monitored past the final visit can be followed via telephone – a repeat Termination/Final Follow-up visit does not need to occur.

Each Clinical Study Site Investigator and research team (co-Investigators, research nurse, clinical trial coordinator) are responsible for identifying and reporting AEs and determining the relationship of the event to the study drug. Aggregate reports blinded by treatment group, detailed by severity, attribution (expected or unexpected), and relationship to the study drug, will be available from the DCC for review by the IMM. A separate report detailing protocol compliance will also be available monthly from the DCC for review by the Protocol PI, who will provide feedback to individual sites as needed. The Protocol Steering Committee (PSC) will advise the Protocol PI as to whether the protocol or informed consent document requires revision based on these reports.

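### The whole-study adverse-event comparison in 9.7 puts crossover children in both columns and ignores unequal time on treatment, so its independent-groups chi-squared test has no valid error rate

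*Combined protocol and SAP*

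**What the plan says.** Section 9.7 sets out two AE comparisons. The first is between the randomised groups over the 8-month placebo-controlled period. The second takes AEs from the whole study, "compared across the entire study duration divided based on treatment-assignment at the time of the AE". AEs seen in fewer than 5% of the cohort, or that look alike in the two groups, go no further. More frequent AEs that appear to differ "for either set of comparator groups will be formally compared statistically using a chi-squared analysis". The test is therefore assigned to both comparisons. Section 9.7 names no pairing, clustering, period or time-at-risk term. It adds longitudinal analyses, but only to see whether AEs already more frequent on AFQ056 increase with time on treatment.

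The design determines who is in each column:

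- Section 3: children "will enter a single-blind 4-month placebo lead-in, followed by an 8-month placebo-controlled phase".
- Section 9.1: "100 subjects with FXS will have AFQ056 baseline assessments and be randomized 1:1 to AFQ056 or placebo".
- Section 3: after month 8, "all subjects will enter the extension and be treated with active drug".
- Section 9.9: "Subjects will be monitored for AEs from the time they sign consent until the final Study visit", so lead-in AEs are on record.
- Section 2.1: drug exposure in the extension runs "up to 16 months in those treated with drug during the first period".

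The Synopsis and section 3 allow the extension to be shortened, or absent, for late enrollees. Section 4.4.1 expects 80 to 90% retention. Section 9.5.3 describes the AE comparison differently: the main and extended phases are examined separately. Section 9 leaves detail to a formal SAP.

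**The concern.** A chi-squared test on two columns assumes that the columns come from different people observed under comparable conditions. The second comparison meets neither assumption.

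First, a placebo-arm child who enters the extension supplies placebo time and then drug time. If lead-in AEs count, so does every child who goes on to take drug. A child prone to insomnia or vomiting tends to raise both columns, so the difference between them varies less than the test supposes.

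Second, the drug column has more time at risk. For an AE that can occur at any time, more children will have had it on drug even if the drug does nothing. In children who cross over, placebo time also always comes before drug time, so any shared change in AE reporting over the study is confounded with treatment.

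Long-term safety in young children is a stated secondary objective (1.3.1) and a stated purpose of the extension (2.1). A misleading p-value here could hide a real signal or create a false one.

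**Working it through.** The plan gives no alpha, AE rate, within-child correlation or power for this comparison, so there is no planned figure to reproduce. The assumptions below are a two-sided 5% test, each child counted once per column for a given AE, and the full schedule without dropout.

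**Step 1: overlap alone, equal follow-up per column.** Let nP and nD be the column sizes, s the number of shared children and ρ the within-child correlation. With equal risk p in both columns:

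- variance assumed by the test: p(1−p)(1/nP + 1/nD)
- true variance: the same minus 2ρ·p(1−p)·s/(nP·nD)
- ratio of true to assumed: 1 − 2ρs/(nP + nD)
- actual alpha: 2[1 − Φ(1.96/√ratio)]

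Without the lead-in, (nP, nD, s) = (50, 100, 50) and the ratio is 1 − 2ρ/3. With it, (100, 100, 100) gives 1 − ρ. For example, at ρ = 0.5 without the lead-in the ratio is 0.667, 1.96/√0.667 = 2.40, and alpha is 1.6%.

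| Assumed ρ | 50 vs 100, 50 shared | 100 vs 100, all shared |
|---|---|---|
| 0 | 5.0% | 5.0% |
| 0.2 | 3.5% | 2.8% |
| 0.3 | 2.8% | 1.9% |
| 0.5 | 1.6% | 0.6% |

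In this setting the test is conservative.

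**Step 2: exposure on the full schedule.**

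- Drug: 50×16 + 50×8 = 1200 person-months.
- Placebo without lead-in: 50×8 = 400.
- Placebo with lead-in: 50×12 + 50×4 = 800.

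**Step 3: effect of that exposure with no drug effect.** Take a constant hazard and an 8-month risk of 20%.

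- The 16-month risk is 1 − 0.8² = 36%, so the drug column averages (20 + 36)/2 = 28% against 20% on placebo.
- Pooled risk is (10 + 28)/150 = 0.253, the standard error is √(0.253×0.747×0.03) = 0.075, and 0.08/0.075 = 1.06. The chance of a false harm signal is about Φ(1.06 − 1.96) = 18%.
- With the lead-in, the placebo column averages the 12-month risk (28.4%) and the 4-month risk (10.6%), giving 19.5%. The standard error is √(0.2375×0.7625×0.02) = 0.060, the ratio is 1.41, and the chance is about 29%.

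A simulation with the same exposures, gamma frailty linking each child's two columns, and no drug effect gave these false-positive rates, nearly all in the harm direction:

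| 8-month risk | Frailty | Lead-in not counted | Lead-in counted |
|---|---|---|---|
| 10% | none | 11% | 17% |
| 10% | moderate (gamma shape 1) | 9% | 14% |
| 20% | none | 18% | 29% |
| 20% | moderate (gamma shape 1) | 13% | 22% |

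With much stronger frailty (within-child correlation of about 0.34 or more) the rate falls below 5% when the lead-in is not counted. With the lead-in counted this takes a correlation of about 0.67.

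**Step 4: what a period-adjusted model can offer.** All children are on placebo in the lead-in and all are on drug in the extension, so treatment varies within a period only in the blinded phase. A generalised least squares calculation with three periods and exchangeable correlation 0.2 to 0.5 gives power of 47 to 61% for 15% versus 30%, and 31 to 41% for 10% versus 20%. The unadjusted chi-squared test has 74 to 79% for 15% versus 30% when the lead-in is counted and follow-up is equal, but only by treating placebo-then-drug time as if it were randomised.

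**The case against.** A reader might infer that the test simply loses power to detect harm. The documents do not support that in general. It follows if AEs are positively correlated within child and follow-up per column is similar, as it might be for early titration effects; section 7 describes paediatric PK-study side effects as typically brief and confined to the first day or two of dosing. For AEs that accrue, unequal exposure pushes the other way and usually dominates.

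A reader might also expect a matched analysis to recover a large power gain: for 15% versus 30% with all children shared and ρ = 0.5, 79% with chi-squared against 95% matched. That comparison has no period term, and step 4 shows that a period-adjusted model does not reach it. In the 50-versus-100 layout, about 8 points of the apparent gain come only from moving from pooled to unpooled variance, since 52% against 60% appears even at zero correlation.

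Other points on the plan's side have weight:

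- Treatment assignment happens only at visit 3, so counting lead-in AEs is not the obvious reading; collection from consent does not settle it.
- Full overlap and the person-month totals are upper bounds, given dropout and shortened extensions.
- This is a secondary comparison, run after a frequency and visual screen.
- It is not the plan's only look at the extension: 9.5.3 examines the extended phase separately, and 9.7 has its longitudinal analyses.
- Section 9 defers detail to a formal SAP.

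These points limit the importance of the problem. They do not remove it, because 9.7 already commits to the chi-squared test for this comparison.

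**Conclusion.** The point holds in a limited form. The whole-study comparison is neither between independent groups nor balanced for time at risk, so the chi-squared test has no valid error rate. Which way it errs depends on AE timing and within-child correlation: the test is conservative for early-onset AEs with similar follow-up (step 1) and prone to false harm signals for AEs that accrue (step 3). Correlation, AE risks, frailty, constant hazard and the 5% level are all assumptions, as the documents give none of them. The figures show the possible range rather than a forecast. The randomised 8-month comparison is unaffected and remains the unbiased safety contrast. The whole-study test should be corrected, but the trial's main safety conclusion does not depend on it.

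**What to change.** 1. Keep the chi-squared or an exact test for the randomised 8-month comparison, and name that as the main safety contrast.
2. For the whole-study comparison, replace chi-squared with a GEE or mixed model on child-by-period records (lead-in if counted, blinded phase, extension). Include treatment at AE onset, study period as a factor, child as the cluster and log person-time as an offset. Use a log link for counts, or a complementary log-log link for any occurrence, so that the offset yields a rate ratio. Report that ratio with its confidence interval.
3. State whether lead-in AEs enter the placebo column.
4. Reconcile 9.7 with 9.5.3, which keeps the main and extended phases apart.

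The cost is SAP wording and standard code, with no new data. With period in the model the drug effect rests mainly on the randomised phase, so the gain is a valid error rate and less bias rather than more power. Rare events may not support a model and would stay as listings.
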